7.4.3 Sensitivity Analyses

Sharing placebo data across interventions: Existing literature and examination of data from prior asthma studies indicate little impact on placebo response from mode of administration,⁸⁻¹⁰ supporting the plan to include all placebo data for a participant in the efficacy analysis of an intervention the participant receives. Sensitivity analyses will be conducted on all data using the same MMRM approach as described above but with the addition of a fixed effect for mode of administration of test treatment or placebo (oral medication vs injection vs dietary supplement). A p-value for the mode of administration effect of 0.1 or less would suggest that the response to treatment is affected by the mode of administration.

Carry-over effects: Period-specific baseline values of FEV₁, ACQ-6 and the baseline levels of deterioration for CompEx will be analyzed to look for evidence of carry-over effects from one treatment period to another due to the crossover study design. If there is an indication of carry-over effects, an analysis will be performed using the primary analysis models but with the addition of effects corresponding to the treatment a participant received prior to the current treatment to control for the carry-over effect.

Intercurrent Events: Sensitivity analyses will be conducted to assess the sensitivity of the primary efficacy results to the method of missing data handling.

Temporal effects: Sensitivity analyses will be conducted to examine treatment effects estimated only from contemporaneous comparisons. Data from the first treatment period for all participants will form the basis of comparisons of each intervention versus pooled placebo. A second sensitivity analysis will estimate treatment effects based on comparisons between each intervention and pooled placebo in the first period and in the second period, and then averaged across the two periods. For both analyses, results will be compared to those from the primary analysis to better understand the impact of the crossover design on analysis results.

To assess the sensitivity of the primary analysis results to the potential for a ceiling effect in participants' response to treatment over time, an analysis will be conducted to determine whether participants enrolled in the study improve regardless of the interventions they receive. In this analysis, we will compare response to placebo in periods 1 and 2 to response to placebo in periods 3-6 with adjustment for the previous treatment received. Additionally, we will evaluate the association between the period and subject's baseline by fitting a model similar to the primary analysis model with baseline as the outcome and period and previous treatment as covariates.

We will evaluate the impact of dose received on the treatment effect by fitting the primary analysis model while adjusting for dose intensity measured as proportion of the total intended dose received.

7.5 Analysis of Secondary Endpoints

CompEx event rates will be modeled using a log-linear model for mean event count with treatment and period number and subgroup level as covariates, with log follow-up time as an offset variable, and assuming variance proportional to the mean. Subgroup-specific treatment effects will be estimated by including subgroup by treatment interaction. Unstructured variance-covariance matrix across periods will be used.

Secondary endpoints such as pre-BD FVC, post-BD FEV₁, symptom free days (defined using diary/CompEx data), and asthma free days will be analyzed using MMRM as described for the primary efficacy endpoints. Secondary endpoints that correspond to event counts, including asthma-specific ED visits, asthma-specific hospital admissions, and asthma-specific ICU admissions, will be analyzed using a log-linear model for mean event count as described for the CompEx endpoint above, with log follow-up time as an offset variable, and assuming variance proportional to the mean. Generalized estimating equations will be used to estimate regression parameters and compute a robust (sandwich) covariance matrix estimator. In addition, time to first exacerbation will be analyzed using a Cox proportional hazards model.

7.6 Safety Data Analyses

Safety data are evaluated on an ongoing basis. Monthly reports of serious adverse events (SAEs) are provided to all DSMB members, and more comprehensive reports of safety data are provided to the DSMB members for review and discussion at their quarterly meetings. These reports include incidence of treatment-emergent adverse events by assigned treatment group. Adverse events are coded using the Medical Dictionary for Regulatory Activities (MedDRA). Adverse event rates (and severity of non-serious adverse events) are compared between active and placebo periods for each intervention. Note that for a particular intervention, all placebo periods for participants receiving the intervention are included, and not just those where the matching placebo was received.

Based on the results of their review, the DSMB will recommend to the NHLBI whether to continue or discontinue each intervention for safety reasons. In addition, the DSMB monitors all safety data

throughout the course of the trial and will be notified as soon as possible of any SAE that is deemed both unexpected and probably related to treatment (serious, unexpected, suspected adverse reactions or SUSARs).

The PrecISE Medical Monitor reviews lab abnormalities on an ongoing basis that are potentially unblinding to clinical personnel at the site and advises the clinical investigator and staff if follow-up testing or other procedures are needed. Summaries of lab abnormalities are reviewed by the DSMB at their quarterly meetings.

Final safety analyses will be performed for each intervention, once the intervention completes and all follow-up data are obtained. Descriptive summaries (differences from placebo and corresponding 95% confidence intervals, tables and graphs) of safety endpoints, including adverse events, laboratory parameters, and other safety biomarkers, will be generated by test treatment versus placebo.

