### 9.5.3 SAFETY ANALYSES

Safety data will be evaluated on an ongoing basis. Monthly reports of serious adverse events will be provided to the chair of the DSMB. The DSMB will be unblinded to assigned treatment. More comprehensive reports will be provided to all DSMB members on a regular schedule as determined by the DSMB. These reports will include incidence of treatment-emergent adverse events by assigned treatment group. Adverse events will be coded using the Medical Dictionary for Regulatory Activities (MedDRA). Adverse event rates (and severity non-serious adverse events) will be compared between active and placebo periods for each intervention. Note that for a particular intervention, all placebo periods for participants receiving the intervention will be included, and not just those where the matching placebo was received.

Based on the results of these reviews, the DSMB will recommend to the NHLBI whether to continue or discontinue each test treatment. In addition, the DSMB will be monitoring all of the safety data throughout the course of the trial and will be notified as soon as possible of any SAE that is deemed both unexpected and related to treatment. All SAEs will be reviewed at each DSMB meeting.

Final safety analyses will be performed for each intervention, once the intervention completes and all follow-up data are obtained. Descriptive summaries (tables and graphs) of safety endpoints, including adverse events, laboratory parameters, and other safety biomarkers, will be generated by test

treatment versus placebo, and hypothesis tests for differences between groups will be generated for selected parameters.

---

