4.3 Assignment of Test Treatment versus Placebo and Masking

Each intervention has its own placebo that matches the test treatment in mode of administration, color, size, and/or taste.

In the first two periods, each participant will receive a test treatment and its matching placebo, with the order being randomly determined (crossover sequence allocation). During subsequent treatment periods (periods 3-6), the placebo assignment probability is initially set to 0.17 but monitored throughout the study and adjusted as needed to yield, on average, approximately 25% of all participants receiving a second placebo. Once a participant receives a 2nd placebo, their probability of receiving placebo in subsequent periods is set to 0 (with some exceptions – see below). This strategy results in

participants enrolled earlier and therefore eligible for more treatment periods having a higher chance of receiving a second placebo than participants enrolled later in the trial.

If a participant discontinues treatment during periods 1 or 2 such that no post-baseline assessments of the FEV₁ percent predicted and ACQ-6 are available, the probability of their receiving placebo in periods 3 and 4 might be adjusted to ensure the participant will have efficacy evaluable data from at least one placebo period during the study. In period 3, the probability of receiving placebo = 0.5, and in period 4, the probability = 0 if placebo is received in period 3, and = 1 otherwise. The participant is also eligible to receive another placebo in periods 5-6 with the same probability as any other participant. A participant may therefore be randomly assigned placebo at most three times during the study and will contribute efficacy data to the statistical analysis from at most two placebo periods.

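### SAP 7.6 compares adverse event rates between active and placebo periods with no stated period adjustment, so part of any time trend in event reporting is attributed to the drug

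*SAP*

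**What the plan says.** SAP 7.6 states that "Adverse event rates (and severity of non-serious adverse events) are compared between active and placebo periods for each intervention". It adds that "all placebo periods for participants receiving the intervention are included, and not just those where the matching placebo was received". The final output is "Descriptive summaries (differences from placebo and corresponding 95% confidence intervals, tables and graphs) of safety endpoints". Protocol 9.5.3 describes the same comparison and adds that "hypothesis tests for differences between groups will be generated for selected parameters". Neither section names a model, a period term, an exposure offset or a restriction to matched pairs.

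The position of placebo is fixed by SAP 4.3: "In the first two periods, each participant will receive a test treatment and its matching placebo, with the order being randomly determined". From period 3 onward the placebo probability starts at 0.17 and is tuned so that about a quarter of participants receive a second placebo.

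Elsewhere the SAP does handle time. In 7.5, CompEx counts use a "log-linear model for mean event count with treatment and period number and subgroup level as covariates", and the healthcare-use counts follow the same form with a robust covariance. In 7.4.1 the primary model has visit nested within period, and 7.4.3 plans temporal sensitivity analyses for efficacy. Nothing extends these to safety.

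**The concern.** Order is randomised only within the pair in periods 1-2. A participant who first gets a drug in period 3, 4, 5 or 6 has already had the first placebo. SAP Table 4 puts the closest placebo in an adjacent period for only 36% of active periods in periods 3-6, so for 64% it is further away. Pooling all active periods against all placebo periods therefore compares later drug time with earlier placebo time.

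If the same person reports fewer events as the study goes on, for example through habituation, part of that fall is credited to the drug and a real excess shrinks. If reporting rises, an excess appears that the drug did not cause. The comparison feeds the periodic summaries to the DSMB and the final safety statement for each intervention.

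**Working it through.** **Inputs from the documents.** 395 participants; 111 per intervention, or 93 where no futility analysis is done (SAP 5, Protocol 9.2); five interventions; two active interventions per participant on average (SAP 5); placebo probability 0.17 and about 25% with a second placebo (SAP 4.3); about 1,000 treatment periods (SAP 1.3).

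**Step 1: reproduce the plan's own figure.** A forward simulation used uniform enrolment over 42 months, a 54-month study, 24-week cycles, 2% dropout per 4 weeks and placebo probability 0.17 from period 3 until a second placebo. It gives 24.7% with a second placebo, against about 25% in the SAP.

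**Step 2: share of active periods that fall in periods 3-6, averaged over interventions.** This assumes that all 395 participants supply one active period in periods 1-2.
- At 111 each: 5 x 111 = 555; (555 - 395) / 555 = 29%.
- At 93 each: 5 x 93 = 465; (465 - 395) / 465 = 15%.
- At two active interventions per participant: 1 of 2 = 50%.
- Cross-check on the 50% case: 2 x 395 = 790 active, plus 395 first placebos and 0.25 x 395 = 99 second placebos, makes 1,284 periods. SAP 1.3 expects 1,000. Working back from 1,000: 1,000 - 395 - 99 = 506 active, and (506 - 395) / 506 = 22%. The 50% case is thus at the high end.

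**Step 3: distortion of the rate ratio.** Let u be the later-drug share and d = 1 - fall, where the fall applies from periods 1-2 to periods 3-6. With no drug effect and a placebo rate of 1 in periods 1-2:
- active mean = (1 - u) + u x d
- placebo mean = 0.75 + 0.25 x (1 + d) / 2, since a quarter of recipients have a late second placebo averaged with the first
- apparent ratio = true ratio x active mean / placebo mean

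For u = 0.29 and a 20% fall: active = 0.71 + 0.29 x 0.8 = 0.942; placebo = 0.75 + 0.25 x 0.9 = 0.975; 0.942 / 0.975 = 0.966; and 1.25 x 0.966 = 1.21.

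**Step 4: error rate and detection.** Assumptions, none from the documents: 1 event per participant-period, Poisson counts with gamma frailty of variance 0.5, a second placebo independent of when the drug was given, and a 95% interval on the paired mean difference. Each setting used 111 participants and 20,000 simulated trials. Detection means that the interval shows a true 25% excess; with no trend it is about 43%.

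| Later-drug share | Fall | Null ratio | True 25% excess appears as | Error (nominal 5%) | Detection |
|---|---|---|---|---|---|
| 15% | 20% / 30% | 0.995 / 0.992 | 24% / 24% | 5% / 5% | 41% / 39% |
| 29% | 10% | 0.983 | 23% | 5-6% | 37% |
| 29% | 20% / 30% | 0.966 / 0.949 | 21% / 19% | 6% / 7-8% | 32% / 26% |
| 50% | 10% | 0.962 | 20% | 6% | 31% |
| 50% | 20% / 30% | 0.923 / 0.883 | 15% / 10% | 9% / 15% | 20% / 11% |

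Where reporting falls, most of the false exclusions of zero favour the drug. At 2 events per period and a 50% share, the error is about 14% and 24-25%.

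**Step 5: does the remedy work?** A Poisson GEE was run with 111 participants, a true ratio of 1.30, a fall of 10% or 20% per period (a steeper pattern than in step 4), and period counts fitted to Table 4, which place 56% of active periods in periods 3-6 (300 runs each). Without period number the estimate is 1.19 or 1.09, with 91% or 72% interval coverage. With period number it is 1.30 in both cases, with 95% or 92% coverage. Periods 1-2 alone return 1.30 under the 20% fall.

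**The case against.** **The method is read from silence.** SAP 7.6 calls the final output descriptive, and the protocol's tests cover unnamed parameters by an unnamed method. This stands: the documents do not rule out adjustment. But 7.6 does state a pooling rule, and the SAP names period where it intends to use it.

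**Only part of a trend leaks in.** A reader might infer that any change in reporting is counted as a drug effect. It is not. The 1:1 sequence balances periods 1-2, and second placebos offset some of the rest, as step 3 shows.

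**The 29% is not a floor for each intervention.** A reader might take it so. It is an average over five interventions; one intervention may lie below it, and the average is 15% at 93 participants each.

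**Dropout does not make the drug look safer.** It is tempting to add loss of event-prone participants as a reason for a fall. Recipients serve as their own controls: someone who leaves before receiving the drug counts on neither side. In a simulation of drug given in period 3 with no trend, frailty-driven dropout left the ratio at about 1.00. Dropout caused by the events themselves raised it to 1.11-1.35, which makes the drug look worse. Only a within-person trend supports the hidden-harm direction.

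**Safety oversight does not rest on this contrast.** Monthly SAE reports, notification of unexpected related SAEs, Medical Monitor laboratory review and the individual stopping criteria in Protocol 7.1.1 are independent of it. This stands, so the documents do not support a claim that participant protection is weakened.

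**Conclusion.** The point holds as a gap in the analysis specification. The planned comparison mixes drug effect with time in study for active periods after period 2, and no section of either document corrects this for safety. The direction of bias is unknown, because the documents report no trend in adverse events.

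The size rests on an assumed trend and on the later-drug share. At 29% and a 20-30% fall the distortion is modest: a 25% excess is seen as 21% or 19%, with error of 6% to 8%. At 50% it is material: 15% or 10%, with error of 9% or 15%. At a 10% fall the error stays at about 6% or below, and at a 15% share the effect is negligible. This is a cheap improvement to make before the final safety analyses, not a flaw that invalidates them.

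**What to change.** In SAP 7.6:
- For common adverse event categories, base the active-placebo comparison and its 95% interval on the log-linear GEE already used in 7.5, with treatment, period number, log time at risk as offset and a robust within-participant covariance.
- Show the randomised period 1-2 crossover comparison beside it.
- Keep the crude pooled table, labelled as description.
- State whether the protocol's tests for selected parameters use the same model.

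The cost is SAP text and reuse of an existing model; no new data are needed. Intervals will be somewhat wider. Rare events cannot support the model and would appear only in the crude and period 1-2 tables. SAE case review and individual safety monitoring do not change.

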**Other criteria for participant discontinuation at any point in the study:**

1. Safety laboratory exclusions as defined in Sections 5.2 and 7.1 that do not resolve in the washout phase that in the judgment of the site physician or Safety Committee constitutes an on-going safety risk for the participant.
2. Participant or parent of participant (for children) withdraws consent or child withdraws assent.
3. Participant becomes pregnant.
4. Study physician determines that continuation in the study is not in the best interest of the participant.
5. Participant suffers life-threatening asthma exacerbation. A life-threatening asthma exacerbation is defined as an ICU admission requiring intubation, hypoxic seizure or loss of consciousness.
6. Frequent asthma exacerbations
  - a. For participants with 3 or fewer asthma exacerbations in the prior year at screening, the participant has five or more exacerbations in one year of the study.
  - b. For participants with 4 or more asthma exacerbations in the prior year at screening, the participant has a 50 percent or greater increase in exacerbations in one year of the study, compared to the prior year at screening.
7. Frequent hospitalizations
  - a. For participants who have 3 or fewer hospitalizations in the prior year at screening, the participant has four or more hospitalizations (greater than 24 hours) in one year of the study.
  - b. For participants who have 4 or more hospitalizations in the prior year at screening, the participant has a 50 percent or greater increase in hospitalizations in one year of the study, compared to the prior year at screening.
8. Participant has a major change in therapy (see Section 6.5.4).

As always, the participant can withdraw consent from the master protocol at any point, and that will lead to discontinuation from the study. At that point, the investigator will make reasonable effort to ensure participant's well-being and safety and provide a termination visit with appropriate documentation.

The site investigator may decide to stop a participant's treatment due to side effects or other safety concerns. In that case, the participant would immediately begin the washout phase and then receive the treatment assigned according to their initial crossover sequence (period 2), or be re-randomized for the next treatment (period 3-6). If a participant elects to withdraw their consent from a treatment, this will result in discontinuation from the entire study.

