### ***Safety Population***

The Safety Population for each intervention will consist of all participants randomized to that intervention who received at least one dose of study medication. This population will form the basis for all safety analyses and selected secondary efficacy analyses of the intervention.

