7.1 Analysis Populations

Screening Population: Participants who are screened but not randomized will be reported, but not included in any efficacy or safety analyses of study data. SAEs occurring during the screening period are monitored and reported to regulatory agencies each month and will be summarized in final study reports.

Safety population: The Safety population for each intervention consists of all participants randomized to that intervention (active or placebo) who received at least one dose of study medication. This population will form the basis for all safety analyses and selected secondary efficacy analyses of the intervention.

Intention-to-Treat (ITT) Population: The ITT population for each intervention will consist of all participants randomized to that intervention. Participants in the ITT population who are also in the target subgroup for an intervention (in either the a priori target subgroup or in the biomarker negative subgroup) will form the basis for the interim futility analysis.

The primary and secondary efficacy analyses will be conducted using a modified intention-to-treat (mITT) population. The mITT population for an intervention consists of participants who are randomized to the intervention, receive study drug, and contribute at least one post-baseline measurement for each of the primary endpoints during the treatment period in which the participant is randomized to the intervention.

Per-Protocol Population: The per protocol population for each intervention consists of all participants in the mITT population who complete study treatment and are in reasonable compliance with the protocol during the treatment period in which the participant received the intervention. For per protocol analysis purposes, we define compliance as:

- For MCT, clazakizumab, Broncho-Vaxom and cavosonstat, the per-protocol population will include participants completing at least 14 weeks of treatment. In addition, the percentage of intended dose of the study drug taken over the course of follow up is at least 60% for MCT, at

least 75% for clazakizumab (at least 3 out of 4 injections), and 90% for Broncho-Vaxom and cavosonstat.

- For imatinib, the per-protocol population will include participants completing at least 8 weeks of treatment and the end of treatment visit. Additionally, participants should have reached the target dose of 400 mg at least 4 weeks before the end of treatment.

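### The placebo side of the per-intervention safety comparison is selected on staying in the study, so adverse events that end participation are under-counted there

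*SAP*

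**What the plan says.** **The comparison.** SAP 7.6 states: "Adverse event rates (and severity of non-serious adverse events) are compared between active and placebo periods for each intervention". It then adds that "for a particular intervention, all placebo periods for participants receiving the intervention are included, and not just those where the matching placebo was received". Protocol 9.5.3 has the same note: "all placebo periods for participants receiving the intervention will be included, and not just those where the matching placebo was received". In both documents the note stands in the paragraph on ongoing monitoring and DSMB reports. The separate paragraph on the final safety analysis contrasts test treatment with placebo and does not say which placebo periods enter.

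**The population.** SAP 7.1 defines the Safety population as "all participants randomized to that intervention (active or placebo) who received at least one dose of study medication" and adds: "This population will form the basis for all safety analyses". Protocol 9.4 has "all participants randomized to that intervention who received at least one dose of study medication", without the words in brackets.

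**What ends participation.** Protocol 7.2 lists criteria for leaving the study, among them "Participant suffers life-threatening asthma exacerbation" and a major change in therapy. When the investigator stops treatment only, for side effects, the participant goes into washout and on to the next period.

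**Design.** Periods 1-2 use drug-then-placebo (T:P) or placebo-then-drug (P:T) with equal probability (SAP 4.1). In periods 3-6 the placebo probability starts at 0.17, and someone who completes the placebo matched to an intervention cannot later be given that intervention (SAP 4.3). Protocol 4.1 shares placebo data across interventions on purpose, for safety as well as efficacy.

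**The concern.** A drug period is counted because it was started. A placebo period is counted because of something else that happened to the participant, and that depends on remaining in the study. This acts in two ways.

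- **Placebo first, then drug.** Under the literal wording, a P:T participant whose event on placebo ends participation never receives the drug, so that placebo period and its event are left out. The same event on drug in a T:P participant is counted.
- **Borrowed placebo periods.** When an intervention is first assigned in periods 3-6, the participant's earlier placebo periods are added to its comparison. The participant was still there to be randomised, so none of those periods can contain a study-ending event. They add denominator only.

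Both work against the drug, and both concern the gravest events. The DSMB uses this comparison when it advises whether an intervention continues. A harmless drug could show an excess of study-ending events, and a real reduction in them could be hidden.

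**Working it through.** **1. The plan's withdrawal figure.** Protocol 9.2 gives 0.02 per 4 weeks, about 24% per year. Check: 1 - 0.98^13 = 23.1%, and the simple sum 12 x 0.02 = 24%. The figure is reproduced. Over one 16-week period it is 1 - 0.98^4 = 7.8%. Over 24 weeks (period plus 8-week washout) it is 1 - 0.98^6 = 11.4%.

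**2. Periods 1-2, literal reading.** Let N participants start each sequence, h be the chance of a study-ending event per period (equal on drug and placebo), and s the chance of going on to start period 2.

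- Drug: N + Ns periods, h(N + Ns) events, rate h.
- Placebo, T:P: Ns periods, hNs events.
- Placebo, P:T, counted only if the drug is reached: Ns periods, 0 events.
- Placebo rate: hNs / 2Ns = h/2. The ratio is 2.0 for any h and s.
- Share of placebo events lost: hN / (hN + hNs) = 1/(1 + s). With s = 0.886 this is 53%; simulation gave 51-53%.

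**3. Periods 1-2, SAP 7.1 reading, matched placebo only.** Every started placebo period counts, so the placebo rate is h and the ratio is 1.0.

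**4. All periods, no true effect.** The simulation used 395 participants, five interventions with equal assignment, 1:1 sequences, placebo probability 0.17 from period 3 (none after a second placebo), 8-week washout and the plan's withdrawal rate, with 400 replicates. The documents do not say what share of withdrawals are adverse events; 25% and 100% were tried. Participant availability was varied to bracket the SAP's 1000 treatment periods (1.3) and two active interventions per participant (section 5). The six-period runs gave gaps between active and nearest placebo of 34-39 / 30-38 / 17-19 / 5-12 / 0-6%, against 36 / 38 / 17 / 7 / 2% in SAP Table 4.

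Drug/placebo ratio for study-ending events (true value 1.0):

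| Periods in trial | Active per participant | Literal | SAP 7.1 plus all their placebo | By randomised matching placebo |
|---|---|---|---|---|
| 986 (25% of withdrawals are events) | 1.46 | 2.64 | 1.51 | 0.96 |
| 986 | 1.46 | 2.79 | 1.57 | 0.99 |
| 1187 | 1.90 | 3.15 | 1.92 | 0.99 |
| 1254 (at most four periods) | 2.03 | 3.26 | 1.98 | 1.00 |
| 1335 | 2.22 | 3.38 | 2.13 | 1.00 |
| 1787 | 3.23 | 3.78 | 2.58 | 1.01 |

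**5. One run in counts per intervention** (1187 periods, every withdrawal an event).

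- Drug: 11.7/150.1 = 7.8%.
- Placebo, literal: 4.5/181.5 = 2.5%.
- Placebo, SAP 7.1: 8.6/211.5 = 4.1%.
- Placebo matched to the intervention: 6.8/87.2 = 7.8%.
- Borrowed placebo, by subtraction of the last two: 1.8 events in 124.3 periods = 1.4%.

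The borrowed periods carry the residual bias. Their few events come from placebo periods that followed the drug. For drug assigned in periods 3-6 alone, the ratio is about 8-17 on the literal reading and 5-6 under SAP 7.1.

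**6. Other AEs.** With an assumed 0.5 to 2 other AEs per period, the all-AE rate ratio is 1.01-1.12 literal and 1.00-1.10 under SAP 7.1.

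**The case against.** **SAP 7.1 answers the literal reading.** Its Safety population includes participants who had only the placebo and is the basis for all safety analyses. Usage elsewhere is mixed. SAP 4.1 speaks of receiving an intervention before active or placebo is decided; protocol 7.1.2 separates receiving the intervention from receiving its matching placebo. This stands as an ambiguity, so the literal reading cannot be treated as settled. It does not remove the borrowed-period bias.

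**Stronger readings a reader might infer, which the documents do not support:**

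- *A placebo period counts only if the drug came afterwards.* T:P placebo periods and later second placebos follow the drug and are counted with their events.
- *The DSMB cannot see these events.* It receives monthly SAE reports, reviews all SAEs at each meeting and is told promptly of unexpected related ones. One summary is distorted; no event is hidden.
- *The final report necessarily carries the bias.* The inclusion note is in the monitoring paragraph only, so carry-over is an inference.
- *The whole AE profile is distorted.* Step 6 shows that it is not. Events that stop treatment only leave the participant in the comparison. Frequent exacerbations and hospitalisations are judged over a year, so they fit the mechanism less neatly, and a participant with a major change in therapy may re-enter as a new participant.

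**The absolute size may be small.** SAP 7.6 reports differences with 95% intervals. A separate simulation with an assumed event rate of 2% per period gave placebo rates of 0.0103-0.0127 under SAP 7.1 against 0.020 on drug, a bias of 0.7-1.0 percentage points. The 95% half-width is about 1.96 x sqrt(0.020 x 0.980/150 + 0.0115 x 0.9885/212) = 2.7 points. This stands, and it limits the urgency.

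**The bias is conservative.** This does not stand. With 2% and 5% event rates, a drug that truly halves study-ending events showed ratios of 1.5-1.7 literal and 0.9-1.1 under the broader reading.

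**Conclusion.** The stated rule gives a biased active-versus-placebo comparison for events that end study participation, and the bias runs against the drug on either reading. With no true effect the ratio is about 2.6-3.8 literally and 1.5-2.6 under SAP 7.1; near the planned two active interventions per participant it is about 3.2-3.3 and 1.9-2.0. The factor of 2 for periods 1-2 on the literal reading needs only an equal event rate in both periods and arms. The other figures rest on a constant event rate, equal assignment among the five interventions and an assumed event share of withdrawals. The direction does not depend on the values tried.

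The scope is narrow: study-ending events in one comparison. Overall AE rates are nearly unaffected and individual SAE review is intact. It merits correction, but is not a serious threat to safety oversight.

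**What to change.** 1. In SAP 7.6 and protocol 9.5.3, state that the comparison uses the Safety population of SAP 7.1, so that participants who received only the matching placebo count.
2. For deaths, SAEs and AEs leading to study withdrawal, make the main comparison one that counts every started period by randomisation to that intervention, active or matching placebo, whether or not the other period was reached. Stratify by period (1, 2, 3-6), because the placebo share differs. An alternative is all placebo periods in the trial with adjustment for period, limited to participants eligible for the intervention, since three of the five are adults-only.
3. Keep the comparison with all placebo periods of recipients for other AEs, or as supportive. This respects the shared-placebo design.
4. State that the same rule applies to the DSMB reports and the final safety analysis.

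The cost is wording in two sections and one changed table program, with no new data. The downside is precision: with a placebo probability of 0.17 in periods 3-6, few matching placebo periods exist there, so intervals for drugs given in those periods will be somewhat wider. In the run shown in counts, 87 placebo periods per intervention remain instead of 212.
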